#### **7.4 Clinical Laboratory Tests (Serum Chemistry, Hematology, Coagulation, and Urinalysis)**

All clinical laboratory test results will be presented in by-subject data listings, however, only serum chemistry, hematology, coagulation and urinalysis values will be summarized.

Hematology, coagulation, serum chemistry and urinalysis tests will be conducted at the following time points:

**Table 7.4 Lab Test Time Points**

Period	Period Day
Screen	Screening
1	Day -1*
1	Day 4*
1	Day 7*

2	Day 4*
2	Day 7*
3	Day 4**
3	Day 7**
4	Day 4**
4	Day 8***

\* performed following a fast of at least 8 hours  
\*\* performed prior dosing of omeprazole  
\*\*\* performed at the end of Period 4 or prior to Early Termination (ET)

Out-of-normal range (OOR) flags will be recorded as follows: high (H) and low (L) for numerical results and did-not-match (\*) for categorical results. If a value fails the reference range, it will automatically be compared to a computer clinically significant (CS) range suggested by the PI (Celerion SOP GSOP.10.1028). If the value falls within the computer CS range, it will be noted as "N" for not clinically significant. If the value fails (i.e. falls outside of the CS range) the computer CS range, it will be flagged with a "Y" which prompts the PI to determine how the OOR value should be followed using 4 Investigator flags: "N", not clinically significant, "R", requesting a recheck, "^", checking at the next scheduled visit, or "Y", clinically significant. To distinguish the PI flag from the CS range flags, the PI flags "N" and "Y" will be presented as "-" and "+" in the data listings, respectively. Additionally, a derived flag based on a search of the PI comments for a comment of "CS" or "Clinically Significant" will be used. The derived flag will be populated with "+" if the positive clinically significant determination is found in the comments for cases when the PI flag is populated with a "^" or an "R". In addition, CTCAE Version 5.0 grading (found in NCI CTCAE guidance) will be applied to all out-of-range lab values deemed clinically significant by the investigator or designee which are recorded as AEs. The resulting flag, e.g., G1, will be placed along with the Celerion flags (see shell of Table 14.3.4.4).

Out-of-range values and corresponding recheck results will be listed. Other lab results within this panel and time point will also be listed for this subject. Results that are indicated as CS by the PI (either in the PI flag or in PI comments) will be listed in the table. Out-of-range values laboratory value results which are indicated as CS by the PI will be reported as AEs.

For all laboratory values that are numeric, descriptive statistics (n, mean, SD, minimum, median, and maximum) will be presented for each laboratory test by treatment and time point. Change from baseline (defined below) will also be summarized. In general, postdose unscheduled events or rechecks will not be summarized. Similarly, ET results will not be included in summaries.

For each laboratory test, a shift table will be developed comparing the frequency of the results at baseline (above normal, normal, or below normal) to postdose results for

each part, respectively. For urinalysis tests, the categories are normal and outside normal.

Baseline is Day -1 of Period 1 and Day 7 of previous period for Period 2, 3, 4 and is the last non-missing predose measurement prior to dosing of LOXO-292, including rechecks and unscheduled assessments. Day 7 measurement of Period 1, 2, 3 might be used twice as postdose value of Period 1, 2, 3 and baseline value of Period 2, 3, 4. When serving as baseline of Period 2, 3, 4, the re-check or unscheduled values after Day 7 of Period 1, 2, 3 and prior to LOXO-292 dosing of Period 2, 3, 4 could be used as baseline.

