12.4 Blinding

This is an open-label study.

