Subject Number	Age\$/ Sex	Study Period	Treatment	Day	Hour	Date	Time	Department	Test	Result	Reference Range	Unit
XXX-XXX	XX/X	X	X	-X	-X.XX	DDMMYYYY	HH:MM:SS	Serum Chemistry	Cholesterol	XXX	X - X	mg/dL
				X	XX.XX	DDMMYYYY	HH:MM:SS	Serum Chemistry	Cholesterol	XXX	HYR+G3	X - X
				X	XX.XX	DDMMYYYY	HH:MM:SS	Serum Chemistry	Cholesterol	XXX	HY- G2	X - X
				X	XX.XX	DDMMYYYY	HH:MM:SS	Serum Chemistry	Cholesterol	XXX	HN G1	X - X

Programmer Note: All time points for a subject/test with at least one value deemed as CS by the PI will be presented in this table. If there were no CS values as deemed by PI (i.e., no "CS" or "Clinically Significant" in the PI flag or comment field in the laboratory dataset), then this table will contain only the statement: "There were no laboratory values deemed clinically significant by the PI in the study."

Note: \$ Age is calculated from the date of first dosing

H = Above Reference Range, L = Below Reference Range

Computer: N = Not Clinically Significant, Y = Clinically Significant

PI Interpretation: - = Not Clinically Significant, R = To be Rechecked, ^ = Will be Retested at a Later Event

Treatment A: <description>

Treatment B: <description>

Treatment C: <description>

Treatment D: <description>

Prior to Treatment C or D at Period 3, subjects were administered with multiple daily doses of 40 mg omeprazole (1 x 40 mg capsule) from Day -4 to Day -1 of Period 3.

Program : /CAXXXX/ECR/sas\_prg/stsas/tab/PROGRAMNAME.sas DDMMYYYY HH:MM

Tables 14.3.5.1, 14.3.5.3, and 14.3.5.5 will have the following format.

Page 1 of X

Table 14.3.5.1 Clinical Laboratory Summary and Change from Baseline - Serum Chemistry (Safety Population)

Laboratory Test (unit)	Normal Range#	Time Point	Statistic	Treatment				Change From Baseline			
				A	B	C	D	A	B	C	D
Parameter1 (unit)	XX - XX	Baseline	n	XX	XX	XX	XX				
			Mean	XX.XX	XX.XX	XX.XX	XX.XX				
			SD	X.XXX	X.XXX	X.XXX	X.XXX				
			Minimum	XX.X	XX.X	XX.X	XX.X				
			Median	XX.XX	XX.XX	XX.XX	XX.XX				
			Maximum	XX.X	XX.X	XX.X	XX.X				
		Day 4	n	XX	XX	XX	XX	XX	XX	XX	XX
			Mean	XX.XX	XX.XX	XX.XX	XX.XX	XX.XX	XX.XX	XX.XX	XX.XX
			SD	X.XXX	X.XXX	X.XXX	X.XXX	X.XXX	X.XXX	X.XXX	X.XXX
			Minimum	XX.X	XX.X	XX.X	XX.X	XX.X	XX.X	XX.X	XX.X
			Median	XX.XX	XX.XX	XX.XX	XX.XX	XX.XX	XX.XX	XX.XX	XX.XX
			Maximum	XX.X	XX.X	XX.X	XX.X	XX.X	XX.X	XX.X	XX.X
		Day 7/8\$	n	XX	XX	XX	XX	XX	XX	XX	XX
			Mean	XX.XX	XX.XX	XX.XX	XX.XX	XX.XX	XX.XX	XX.XX	XX.XX
			SD	X.XXX	X.XXX	X.XXX	X.XXX	X.XXX	X.XXX	X.XXX	X.XXX

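### Lab results get a CTCAE grade only when the open-label investigator calls them clinically significant adverse events, so no severity-graded lab summary by treatment is free of that judgment

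*SAP*

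**What the plan says.** SAP section 7.4 describes a chain of flags. A value outside the reference range is marked high or low, and then: "If a value fails the reference range, it will automatically be compared to a computer clinically significant (CS) range suggested by the PI". A value inside that second range is marked N and goes no further. A value outside it is marked Y, which prompts the investigator to choose among not significant, recheck, look again at the next visit, or significant. A search of the investigator's comments can add a plus sign where the choice was recheck or next visit.

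CTCAE version 5.0 grading then "will be applied to all out-of-range lab values deemed clinically significant by the investigator or designee which are recorded as AEs". The section refers to the shell of Table 14.3.4.4 for how the grade is displayed. It also states: "Out-of-range values laboratory value results which are indicated as CS by the PI will be reported as AEs".

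Separately, section 7.4 plans that for numeric tests "descriptive statistics (n, mean, SD, minimum, median, and maximum) will be presented for each laboratory test by treatment and time point", together with change from baseline, and that for each test "a shift table will be developed comparing the frequency of the results at baseline (above normal, normal, or below normal) to postdose results". Post-dose unscheduled and recheck results are in general not summarised, and early-termination results are left out.

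On blinding, protocol section 12.4 says: "This is an open-label study".

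**The concern.** A severity grade is most useful when it is read off the number, because then it does not depend on who looked at the result or what they knew. Under the 7.4 rule it depends on exactly that. A rise in a liver enzyme, amylase or lipase that the investigator marks as not significant receives no grade, whatever its size. The investigator knows which treatment was given and also suggests the computer range that decides whether a value is put forward for a decision.

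The tests at issue matter for this compound. Protocol section 8.1.1 lists pancreas and bone marrow among the main target tissues in both rat and minipig, liver as a possible target in the rat, and raised liver tests as a theoretical risk in humans. Inclusion criterion 4 sets liver tests, amylase and lipase within the upper limit of normal at entry, subject to rechecks, so how far a value rises after dosing is the informative part.

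There is also a programming problem: some shell examples carry grades that the text does not allow.

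**Working it through.** No sample size, power or error rate is involved. The check sets the text against the shells, and then sorts the planned lab outputs by whether they need the investigator's call.

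**Step 1: how many independent conditions the rule has.** The rule asks for an out-of-range value, a call of clinically significant, and an AE record. Since every value called significant is reported as an AE, the last two are one judgment. SAP section 7.3 has the clinical site grade each AE on CTCAE version 5.0. Every lab value that qualifies for a lab grade therefore already has a site-assigned grade, and the lab grade adds no independent severity information.

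**Step 2: decode the shell examples.** H and L are above and below the reference range. N and Y are inside and outside the computer range. The remaining key is "PI Interpretation: - = Not Clinically Significant, R = To be Rechecked, ^ = Will be Retested at a Later Event", and a plus sign means clinically significant.

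| Shell | Flag | Grade shown | Fits the 7.4 rule? |
|---|---|---|---|
| 14.3.4.1, Screen row | HN | G1 | No: never put to the investigator |
| 14.3.4.1, Screen row | HN | none | Yes |
| 14.3.4.1, later row | LY- (two values) | none | Yes |
| 14.3.4.1, later row | LN | none | Yes |
| 14.3.4.4 | HYR+ | G3 | Yes |
| 14.3.4.4 | HY- | G2 | No: investigator says not significant |
| 14.3.4.4 | HN | G1 | No: never put to the investigator |

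Flagged examples: 5 in Table 14.3.4.1 and 3 in Table 14.3.4.4, 8 in all. Graded: 1 + 3 = 4. Of those 4, one fits the rule and three do not. The 4 ungraded examples agree with the rule.

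The Screen-row grade is the hardest to reconcile. Under protocol section 13.2.7.3, only procedure-related events before the first dose are reported as AEs, and everything else goes to medical history.

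The serum chemistry listing shell (Appendix 16.2.8.1.1) repeats the five flags of Table 14.3.4.1 with no grade at all, so the shells also differ from one another.

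**Step 3: sort the by-treatment outputs.**

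- Tables 14.3.5.1, 14.3.5.3 and 14.3.5.5 give descriptive statistics and change from baseline. They need no investigator call and have no severity tiers.
- Tables 14.3.5.2, 14.3.5.4 and 14.3.5.6 give shifts among low, normal and high (normal or outside for urinalysis). They need no investigator call, but a slight and a large elevation both count as H.
- Tables 14.3.1.3 and 14.3.1.4 give AE counts by severity grade and treatment. They are graded, but a lab finding enters only after the investigator's call.

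That is six by-treatment lab tables free of judgment but ungraded, two by-treatment tables that are graded but depend on judgment, and none that is both graded and free of judgment. The first six also generally omit post-dose recheck, unscheduled and early-termination values, which are often taken because something looked abnormal.

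**The case against.** The strongest reply is that the SAP delivers what the protocol asks. Protocol section 13.2.7.3 applies CTCAE to reported signs and symptoms, and section 14.3.2 asks only that labs be summarised by treatment and time point. Safety is a secondary objective with no inference planned (SAP section 7). The grade in 7.4 is an annotation beside listed values, so restricting it does not bias any planned table of lab grades. All of this stands, and it keeps the point small.

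A second reply is that the shells are only layouts; SAP section 10 says they may not reflect every aspect of the study. That is a fair reason to let the text govern, but it is weakened because 7.4 itself sends the reader to the shell of Table 14.3.4.4 for the grade. The note under that shell, "All time points for a subject/test with at least one value deemed as CS by the PI will be presented in this table", explains why rows not called significant appear, but not why they carry a grade. The run G3, G2, G1 could depict an AE resolving, since SAP section 7.3 opens a new record at each change of grade. That is possible, but the G2 value is still marked not significant by the investigator, and the reading cannot explain the Screen row.

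Three stronger conclusions are tempting and should be resisted. A reader might infer that the trial has no judgment-free measure of lab toxicity by treatment; the six tables in Step 3 show otherwise. A reader might infer that large elevations would be visible only in listings; a large scheduled rise would also show in the maximum, the change from baseline and a shift to H. And a reader might infer that the shells apply a rule of grading everything; half of the flagged examples in the two tables carry no grade.

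**Conclusion.** The point holds as a minor one. The 7.4 rule ties the lab grade to unblinded judgment and makes it duplicate the AE grade. Three of the four graded shell examples conflict with it. No planned by-treatment lab summary is both severity-graded and independent of the investigator's call.

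The practical size cannot be estimated. The share of gradable abnormal values left ungraded equals, by definition, the share not called significant. The documents give no figure for it, so it could lie anywhere from 0 to 100%, and any narrower percentage would only restate an assumption. The conclusion rests on reading the flag codes by the SAP's own key and on treating the shells as intended examples. If the shells are treated as pure placeholders, the inconsistency falls away, but the gap in Step 3 remains. Primary PK results are unaffected.

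**What to change.** In SAP section 7.4, replace the grading sentence with one to this effect: CTCAE version 5.0 grades will be derived from the numeric value for every post-dose lab result that can be graded on its value alone, regardless of the investigator's flag or AE status.

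Add one table of maximum post-dose grade per lab test by treatment, counting recheck, unscheduled and early-termination values, and state how each such value is assigned to a treatment. Keep the investigator's flag beside the grade as separate information. Align the shells of Table 14.3.4.1, Table 14.3.4.4 and Appendix 16.2.8.1.1 with the new sentence.

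If the sponsor prefers to keep the present rule, the minimum is to remove the grades that it does not allow from the two table shells. That settles the inconsistency but leaves the gap in the by-treatment outputs.

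The cost is SAP wording, one derivation and one table, using data already collected. There are two small downsides: more Grade 1 flags on trivial deviations, and CTCAE terms that need clinical input cannot be derived from the number and stay outside the table.

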### 7.5 Vital Signs (Blood Pressure, Pulse Rate, Respiration Rate, and Temperature)

Vital signs were performed at the following time points:

**Table 7.5 Vital Signs Time Points**

Period	Period Day	Study Hour	Parameter
Screen	Screening		HR, BP, RR, T
1	Day -1	0*	HR, BP, RR
1	Day 1	2	HR, BP, RR
1	Day 4	72	HR, BP, RR
2	Day 1	0**	HR, BP, RR
2	Day 1	2	HR, BP, RR
2	Day 4	72	HR, BP, RR
3	Day 1	0**	HR, BP, RR
3	Day 1	2	HR, BP, RR
3	Day 4	72	HR, BP, RR
4	Day 1	0**	HR, BP, RR
4	Day 1	2	HR, BP, RR
4	Day 4	72	HR, BP, RR
4	Day 8	168***	HR, BP, RR, T

\* performed within 24 hours prior dosing  
\*\* performed prior dosing  
\*\*\* performed at the end of Period 4 or prior to ET

Descriptive statistics will be reported for vital sign measurements (blood pressure, pulse, and respiration rate) and change from baseline by treatment and time point. Baseline is Day -1 of Period 1 and Day 1 predose of Period 2, 3, 4 and is the last non-missing predose measurement prior to dosing of LOXO-292, including rechecks and unscheduled assessments. Postdose recheck values and ET results will not be used for calculation of descriptive statistics. All vital signs results will be listed by subject.

## 7.6 ECG (Heart Rate, PR, QRS, QT, and QTcF [QT with Fridericia correction])

Single 12-lead ECGs were performed at the following time points:

**Table 7.6: ECG Time Points**

Period	Period Day	Study Hour
Screen	Screening	
1	Day -1	0*
1	Day 1	2
1	Day 4	72
2	Day 1	0**
2	Day 1	2
2	Day 4	72
3	Day 1	0**
3	Day 1	2
3	Day 4	72
4	Day 1	0**
4	Day 1	2
4	Day 4	72
4	Day 8	168***

\* performed within 24 hours prior dosing  
\*\* performed prior dosing  
\*\*\* performed at the end of Period 4 or prior to ET

Descriptive statistics will be reported for ECG parameters and change from baseline by treatment and time point. Baseline is Day -1 of Period 1 and Day 1 predose of Period 2, 3, 4 and is the last non-missing predose measurement prior to dosing of LOXO-292, including rechecks and unscheduled assessments. Postdose recheck values and ET results will not be used for calculation of descriptive statistics. QTcF values that are > 450 msec and increase from baseline > 30 msec will be flagged in the data listing. All ECG interval parameters will be listed by subject and time point of collection.

## 7.7 Prior and Concomitant Medications

All prior concomitant medications recorded during the study will be coded with the WHO Dictionary, Version Mar2017 B3 and listed. Note: Per Exclusion Criterion 15, subjects should refrain from using any drug, including prescription and non-prescription medications, herbal remedies, and vitamin supplements 14 days prior to the first dosing and throughout the study. After dosing, acetaminophen (up to 2 g per 24 hours) may be administered at the discretion of the PI or designee.

## 7.8 Physical Examination

Physical examinations will be performed at screening. Abbreviated physical examinations may be performed at check-in (Day -1) of the first period. Abnormal findings will be reported as medical history or adverse events by the clinical site. Physical examination results will be listed by subject and time point.

## 7.9 Meals

The composition of meals will be provided in the CSR. If the subject only eats part of the meal, the percentage of meals that is not consumed will be documented in the comment field of the Meal Times dataset.

# 8. SUMMARY OF CHANGES FROM PROTOCOL-PLANNED ANALYSIS

The analyses described in this SAP are aligned with those analyses described in the protocol.

# 9. SUMMARY TABLES AND FIGURES

Summary tables and figures are numbered following the International Council for Harmonisation (ICH) structure but may be renumbered as appropriate during the compilation of the tables and figures for the CSR. Note that all summary tables and figures will be generated using SAS® Version 9.3 or higher.

## 9.1 In-text Summary Tables and Figures

The following is a list of table and figure titles that will be included in the text of the CSR. Tables and figures will be numbered appropriately during compilation of the CSR.

### Section 10:

Table 10-1 Summary of Disposition (Safety Population)

### Section 11:

Table 11-1 Demographic Summary (Safety Population)

Table 11-2 Summary of Plasma LOXO-292 Pharmacokinetic Parameters  
Following Administration of 160 mg LOXO-292 Fasted (Treatment A), Administration of 160 mg LOXO-292 Fed (Treatment B), Coadministration of Multiple Dose Omeprazole + 160 mg LOXO-292 Fasted (Treatment C), and Coadministration of Multiple Dose Omeprazole + 160 mg LOXO-292 Fed (Treatment D)  
(Pharmacokinetic Population)

Table 11-3      Summary of Statistical Comparisons of Plasma LOXO-292 Pharmacokinetic Parameters Following Administration of 160 mg LOXO-292 Fed (Treatment B) Versus Administration of 160 mg LOXO-292 Fasted (Treatment A) (Pharmacokinetic Population)

Table 11-4      Summary of Statistical Comparisons of Plasma LOXO-292 Pharmacokinetic Parameters Following Coadministration of Multiple Dose Omeprazole + 160 mg LOXO-292 Fasted (Treatment C) Versus Administration of 160 mg LOXO-292 Fasted (Treatment A) (Pharmacokinetic Population)

Table 11-5      Summary of Statistical Comparisons of Plasma LOXO-292 Pharmacokinetic Parameters Following Coadministration of Multiple Dose Omeprazole + 160 mg LOXO-292 Fed (Treatment D) Versus Administration of 160 mg LOXO-292 Fed (Treatment B) (Pharmacokinetic Population)

Table 11-6      Summary of Statistical Comparisons of Plasma LOXO-292 Pharmacokinetic Parameters Following Coadministration of Multiple Dose Omeprazole + 160 mg LOXO-292 Fed (Treatment D) Versus Coadministration of Multiple Dose Omeprazole + 160 mg LOXO-292 Fasted (Treatment C) (Pharmacokinetic Population)

Figure 11-1      Arithmetic Mean Plasma LOXO-292 Concentration-Time Profiles Following Administration of 160 mg LOXO-292 Fasted (Treatment A), Administration of 160 mg LOXO-292 Fed (Treatment B), Coadministration of Multiple Dose Omeprazole + 160 mg LOXO-292 Fasted (Treatment C), and Coadministration of Multiple Dose Omeprazole + 160 mg LOXO-292 Fed (Treatment D) (Pharmacokinetic Population)

Section 12:

Table 12-1      Treatment-Emergent Adverse Event Frequency by Treatment – Number of Subjects Reporting the Event (% of Subjects Dosed) (Safety Population)

## 9.2      Section 14 Summary Tables and Figures

The following is a list of table and figure titles that will be included in Section 14 of the report. Table and figure titles may be renumbered as appropriate during the compilation of the report.

### 14.1      Demographic Data Summary Tables

#### 14.1.1      Demographic Tables

Table 14.1.1.1 Summary of Disposition (Safety Population)

Table 14.1.1.2 Disposition of Subjects (Safety Population)

Table 14.1.1.3 Demographic Summary (Safety Population)

## 14.2 Pharmacokinetic Data Summary Tables and Figures

### 14.2.1 Plasma LOXO-292 Tables

Table 14.2.1.1 Plasma LOXO-292 Concentrations (ng/mL) Following Administration of 160 mg LOXO-292 Fasted (Treatment A) (Pharmacokinetic Population)

Table 14.2.1.2 Plasma LOXO-292 Concentrations (ng/mL) Following Administration of 160 mg LOXO-292 Fed (Treatment B) (Pharmacokinetic Population)

Table 14.2.1.3 Plasma LOXO-292 Concentrations (ng/mL) Following Coadministration of Multiple Dose Omeprazole + 160 mg LOXO-292 Fasted (Treatment C) (Pharmacokinetic Population)

Table 14.2.1.4 Plasma LOXO-292 Concentrations (ng/mL) Following Coadministration of Multiple Dose Omeprazole + 160 mg LOXO-292 Fed (Treatment D) (Pharmacokinetic Population)

Table 14.2.1.5 Plasma LOXO-292 Pharmacokinetic Parameters Following Administration of 160 mg LOXO-292 Fasted (Treatment A) (Pharmacokinetic Population)

Table 14.2.1.6 Plasma LOXO-292 Pharmacokinetic Parameters Following Administration of 160 mg LOXO-292 Fed (Treatment B) (Pharmacokinetic Population)

Table 14.2.1.7 Plasma LOXO-292 Pharmacokinetic Parameters Following Coadministration of Multiple Dose Omeprazole + 160 mg LOXO-292 Fasted (Treatment C) (Pharmacokinetic Population)

Table 14.2.1.8 Plasma LOXO-292 Pharmacokinetic Parameters Following Coadministration of Multiple Dose Omeprazole + 160 mg LOXO-292 Fed (Treatment D) (Pharmacokinetic Population)

Table 14.2.1.9 Intervals (Hours) Used for Determination of Plasma LOXO-292 *Ket* Values Following Administration of 160 mg LOXO-292 Fasted (Treatment A), Administration of 160 mg LOXO-292 Fed (Treatment B), Coadministration of Multiple Dose Omeprazole + 160 mg LOXO-292 Fasted (Treatment C), and Coadministration of Multiple Dose Omeprazole + 160 mg LOXO-292 Fed (Treatment D) (Pharmacokinetic Population)

Table 14.2.1.10 Statistical Comparisons of Plasma LOXO-292 Pharmacokinetic Parameters Following Administration of 160 mg LOXO-292 Fed (Treatment B) Versus Administration of 160 mg LOXO-292 Fasted (Treatment A) (Pharmacokinetic Population)

Table 14.2.1.11 Statistical Comparisons of Plasma LOXO-292 Pharmacokinetic Parameters Following Coadministration of Multiple Dose Omeprazole + 160 mg LOXO-292 Fasted (Treatment C) Versus Administration of 160 mg LOXO-292 Fasted (Treatment A) (Pharmacokinetic Population)

Table 14.2.1.12 Statistical Comparisons of Plasma LOXO-292 Pharmacokinetic Parameters Following Coadministration of Multiple Dose Omeprazole + 160 mg LOXO-292 Fed (Treatment D) Versus Administration of 160 mg LOXO-292 Fed (Treatment B) (Pharmacokinetic Population)

Table 14.2.1.13 Statistical Comparisons of Plasma LOXO-292 Pharmacokinetic Parameters Following Coadministration of Multiple Dose Omeprazole + 160 mg LOXO-292 Fed (Treatment D) Versus Coadministration of Multiple Dose Omeprazole + 160 mg LOXO-292 Fasted (Treatment C) (Pharmacokinetic Population)

